5.3. Secondary Endpoint(s) Analyses

The PK analyses will be based on the pharmacokinetic analysis set.

5.3.1. Definition of Pharmacokinetic endpoint(s)

- Blood: plasma ratio of [¹⁴C]-GSK3640254 – related materials (total radioactivity)

5.3.1.1. Derived plasma pharmacokinetic parameters

The blood: plasma ratio of total radioactivity will be calculated in period 2 according to the following equation:

Ratio $C_b/C_p = \text{Radioactivity Concentration in blood (C}_b\text{)} / \text{Radioactivity Concentration in plasma (C}_p\text{)}$

5.3.2. Main analytical approach

The blood: plasma ratio of total radioactivity (C_b/C_p) will be calculated at each time point and will be summarized and reported by Pharmaron.

5.4. Exploratory Endpoint(s) Analyses

The PK analyses will be based on the pharmacokinetic analysis set.

5.4.1. Definition of Pharmacokinetic endpoint(s)

- Characterization and quantification of metabolites in plasma, urine, faecal and duodenal bile (qualitative identification in bile). These analytical investigations will be conducted, and the results reported under a separate nonclinical GSK protocol
- AUC (0-∞), AUC(0-t), and C_{max} for the evaluation of the PK and the relative bioavailability of GSK3640254 following administration of the 85mg suspension compared to the 200 mg tablet

5.4.1.1. Metabolite profiling analyses in plasma, urine, feces and bile

The metabolic profiling/structural characterization aspect of this work will be performed by GSK (or a GSK representative) in a separate DMPK study report. Data from the quantification of unchanged GSK3640254 in urine following IV administration will be used in the estimate of renal clearance, as detailed above.

5.4.1.2. Derived plasma pharmacokinetic parameters

The PK parameters for GSK3640254 following oral administration of a 200 mg tablet or of 85 mg suspension will be reported as described in Section 5.2. Subsequently, the following parameters will be used for the assessment of the relative bioavailability of GSK3640254 following administration of the 85 mg suspension compared to the 200 mg tablet as described in Section 5.4.2.

5.4.2. Main analytical approach

Table 7 Statistical methodology specification

The following pharmacokinetic statistical analyses will only be performed if sufficient data is available (i.e. if participants have well defined plasma profiles).

Endpoint / Variables
Derived PK parameters: 
 • $AUC_{(0-inf)}$ • $AUC_{(0-t)}$ • C_{max}
Model Specification

 • To evaluate the relative bioavailability of GSK3640254 following administration of the 85 mg suspension compared to the 200 mg tablet, the PK parameters will be analysed using a mixed effect model as described below: $\log_e(\text{PK parameter}) = \beta_0 + \gamma_i + \tau_j + \varepsilon_{ij}$ where, 
 β_0: intercept γ_i: random effect for i^{th} participant, following $N(0, \sigma^2)$ τ_j: treatment effect ($j = 85 \text{ mg suspension or } 200 \text{ mg tablet Treatment}$) ε_{ij}: random error for participant i, treatment effect j, following $N(0, \sigma_w^2)$. • The model parameters will be estimated using Restricted Maximum Likelihood with the Newton-Raphson algorithm. • The Kenward-Roger degree of freedom approach will be used. • Given the random effect for subject "i", the random error is assumed to be independently distributed within the subject. • The least square means for each treatment formulation (85 mg suspension and 200 mg tablet) will be estimated based on the fitted model. The mean difference between the treatment formulations (85 mg suspension and 200 mg tablet) and its 90% CIs will be also estimated using the within-subject variance. • The estimates of least square means for each treatment formulation, the treatment difference between treatment formulations and the 90% CIs will be exponentially back-transformed to obtain the estimates of geometric means of $AUC_{(0-t)}$, $AUC_{(0-inf)}$ and C_{max} for each treatment formulation, the ratio of geometric means (85 mg suspension and 200 mg tablet) and its 90% CIs, respectively. • Within-subject variability (%CVw) for the PK parameters will be estimated using within-subject variance from the analysis model as follows: $\%CVw (\%) = [\exp(\sigma_w^2) - 1]^{1/2} \times 100$

Model Checking & Diagnostics

In case there is a problem with model convergence, the arithmetic means for \log_e -transformed $AUC_{(0-t)}$ and C_{max} and the treatment differences (85 mg suspension and 200 mg tablet) within each participant will be calculated using only data from the participants who have completed both the periods for 85 mg suspension and 200 mg tablet. The mean treatment difference and paired-t test based 90% CIs for treatment difference in \log_e scale will be estimated. The results will be provided in an exponentially back-transformed scale.

Model Results Presentation

Based on the relative bioavailability, the bioequivalence between 85 mg suspension and 200 mg tablet will be evaluated as follows:

- The bioequivalence is established when the 90% CI of the ratio for $AUC_{(0-t)}$, $AUC_{(0-inf)}$ and C_{max} between treatment formulations (85 mg suspension and 200 mg tablet) are within the range of 0.80 to 1.25.

5.5. (Other) Safety Analyses

The safety analyses will be based on the Safety analysis set, unless otherwise specified.

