1.3. Study Design

Overview of Study Design and Key Features	

Screening: up to 30 days before first dose
 
Treatment Period 1 (Inpatient): [¹⁴C]GSK3640254 IV microtracer dose concomitant with oral tablet GSK3640254 dose. Sample collection for 7 days after dosing.
 
At least 13 days washout between doses.
 
Treatment Period 2 (Inpatient): Single oral dose of [¹⁴C]GSK3640254. Sample collection for 7 – 14 days after dosing*.
 
Follow up: 7 – 14 days after the last assessment.
 
*If radioactivity in the 24 hour interval collections immediately prior to discharge is still >1%, faecal samples will be collected by participants at home after Day 15 (day of discharge/follow up)
	
Design Features	
 • Open-label • Single center • Non-randomised • 2-period, single-sequence • Mass balance study • Approximately 6 healthy male participants will be enrolled • A screening visit (up to 30 days before first dose) • Two inpatient treatment periods (Treatment Periods 1 and 2), with at least 13 days between doses. 
A follow-up visit 7 – 14 days after the last assessment in Treatment Period 2

Study intervention	
Study intervention Assignment	
Approximately six participants will be enrolled to achieve at least 4 participants completing the two treatment periods. On Day 1 of Treatment Period 1, after an overnight fast of at least 8 h, each participant will take a single 200 mg oral dose (2 x 100 mg tablets) of GSK3640254 with a moderate fat meal (approximately 600 calories with approximately 30% of calories from fat); the IV infusion of 100 µg of [¹⁴C]-GSK3640254 (approximately 3.7 kBq; 100 nCi) will begin 5 h after oral dose and continue over 1 h. On Day 1 of Treatment Period 2, after an overnight fast of at least 8 h, each participant will receive approximately 85 mg [¹⁴C]-GSK3640254 (approximately 3.15 MBq; 85 µCi) as an oral suspension with a moderate fat meal (approximately 600 calories with approximately 30% of calories from fat).

Interim Analysis	There will be no formal interim analyses.

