ML(iv)	
Metabolite load following intravenous administration, calculated as:
 $ML(iv) = \frac{[\text{Total Radioactivity AUC}(0 - \infty) - [^{14}\text{C}]GSK3640254 \text{ AUC}(0 - \infty)]}{\text{Total Radioactivity AUC}(0 - \infty)}$ 
Treatment Period 1

ML(po)	
Metabolite load following oral administration, calculated as:
 $ML(po) = \frac{[\text{Total Radioactivity AUC}(0 - \infty) - GSK3640254 \text{ AUC}(0 - \infty)]}{\text{Total Radioactivity AUC}(0 - \infty)}$ 
Treatment Period 2
 
Note: GSK3640254 AUC(0-∞) may be updated depending on the sample analysis conducted but refers to the parent GSK3640254 from oral dose

Fg	
Fraction metabolized by gut wall as a fraction of the oral dose, calculated as:
 $Fg = 1 - [ML(po) - ML(iv)]$

CONFIDENTIAL

Statistical Analysis Plan 213051

Parameter	Parameter Description
$CL_{h,iv,blood}$	
Hepatic blood clearance, calculated as:
 $CL_{h,iv,blood} = CL_{h,iv,plasma} * \text{blood to plasma ratio}$ 
Where $CL_{h,iv,plasma}$ is the hepatic plasma clearance calculated as:
 $CL_{h,iv,plasma} = CL - CL_r$
E_h	
Hepatic extraction ratio, calculated as:
 $E_H = CL_{h,iv,blood} / Q_h$ 
Where Q_h = hepatic blood flow (literature value of 1660 mL/min, Edginton, 2006)
 
Note: if assumption that hepatic CL accounts for 100% of the clearance (i.e. CL_r is negligible), then $E_h = CL * \text{blood to plasma ratio} * Q_h$

F_h	$F_h = 1 - E_h$
F_a	
Fraction absorbed following an oral dose, calculated as follows
 $F_a = \frac{F(0 - \infty)] / (1 - E_H)}{F_g}$
Dose(iv)	Radiometric IV dose calculated by Covance
Dose(oral)	Radiometric oral dose calculated by Covance
$F(0-\infty)$	
Oral absolute bioavailability based on $AUC(0-\infty)$, calculated as:
 $F(0 - \infty) = \frac{GSK3640254 \text{ AUC}(0 - \infty)(\text{oral})}{\text{Dose}(\text{oral}) \frac{\text{Dose}(\text{iv})}{[14C]GSK3640254 \text{ AUC}(0 - \infty)(\text{iv})}}$ 
Per Subject

CONFIDENTIAL

Statistical Analysis Plan 213051

Parameter	Parameter Description
	Note: Radiometric dose will be used for IV. GSK3640254 AUC(0-∞) (Oral) refers to the parent GSK3640254 from oral dose, but may be updated depending on the sample analysis

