F(0-t)	
Oral absolute bioavailability based on AUC(0-t), calculated as:
 $F(0-t) = \frac{\text{GSK3640254 AUC}(0-t)(\text{oral})}{\frac{\text{Dose}(\text{oral})}{\text{Dose}(\text{iv})} * \frac{[14C]\text{GSK3640254 AUC}(0-t)(\text{iv})}{[14C]\text{GSK3640254 AUC}(0-t)(\text{iv})}}$ 
Per Subject
 
Note: Radiometric dose will be used for IV. GSK3640254 AUC(0-t) (Oral) refers to the parent GSK3640254 from oral dose, but may be updated depending on the sample analysis

CL/F	
Apparent oral clearance, calculated as:
 $CL/F = \frac{\text{Dose}}{AUC(0-\infty)}$
Vz/F	
Apparent volume of distribution based on the terminal phase
 $Vz/F = \frac{\text{Dose}}{[\lambda_z * AUC(0-\infty)]}$
GSK3640254/ Total radioactivity ratio for Cmax	
Cmax Ratio = Exp {[log_e(GSK3640254 Cmax)] - [log_e(Total radioactivity Cmax)]}
 
Per subject for radiolabelled oral dose. GSK3640254 may be updated depending on the sample analysis conducted but refers to the parent GSK3640254 from oral dose

GSK3640254/ Total radioactivity ratio for AUC(0-∞)	
Cmax Ratio = Exp {[log_e(GSK3640254 AUC(0-∞))] - [log_e(Total radioactivity AUC(0-∞))]}
 
Per subject for radiolabelled oral dose. GSK3640254 may be updated depending on the sample analysis conducted but refers to the parent GSK3640254 from oral dose

GSK3640254/ Total radioactivity	
Cmax Ratio = Exp {[log_e(GSK3640254 AUC(0-t))] - [log_e(Total radioactivity AUC(0-t))]}

CONFIDENTIAL

Statistical Analysis Plan 213051

Parameter	Parameter Description
ratio for AUC(0-t)	Per subject for radiolabelled oral dose. GSK3640254 may be updated depending on the sample analysis conducted but refers to the parent GSK3640254 from oral dose
[¹⁴ C]-GSK3640254/ Total radioactivity ratio for Cmax	Cmax Ratio = $\text{Exp} \{[\log_e([\sup{14}\text{C}]\text{-GSK3640254 Cmax}) - [\log_e(\text{Total radioactivity Cmax})]]\}$ Per subject for radiolabelled IV dose
[¹⁴ C]-GSK3640254/ Total radioactivity ratio for AUC(0-∞)	Cmax Ratio = $\text{Exp} \{[\log_e([\sup{14}\text{C}]\text{-GSK3640254 AUC}(0-\infty)) - [\log_e(\text{Total radioactivity AUC}(0-\infty))]]\}$ Per subject for radiolabelled IV dose
[¹⁴ C]-GSK3640254/ Total radioactivity ratio for AUC(0-t)	Cmax Ratio = $\text{Exp} \{[\log_e([\sup{14}\text{C}]\text{-GSK3640254 AUC}(0-t)) - [\log_e(\text{Total radioactivity AUC}(0-t))]]\}$ Per subject for radiolabelled IV dose

Notes:

- Additional parameters may be included as required

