5.2.2. Main analytical approach

A primary objective is to determine parent GSK3640254 and total drug-related radioactivity systemic concentrations following a single IV microtracer dose of [¹⁴C]-GSK3640254 (with an oral dose of non-radiolabelled GSK3640254) and oral dose of [¹⁴C]-GSK36402541. To assess this, the plasma PK parameters: AUC(0–inf), AUC(0–t), C_{max}, t_{max} and t_{1/2} of parent and total drug-related material (radioactivity) will be summarized and listed. The volume V_{ss} and clearance (CL) of parent after IV dose (Period 1 only), renal clearance of parent (CL_r) after both IV and oral dose, oral clearance (CL/F) and apparent volume of distribution (V_z/F) for the parent following oral administration will also be summarized and listed.

To assess the absolute oral bioavailability of GSK3640254 absolute oral bioavailability (F), F_h, F_a and F_g will be summarized and listed.

To determine the rate and extent of excretion of total radioactivity in urine and feces and the total recovery of radioactivity, following IV and oral administrations of [¹⁴C]-GSK3640254 the PK parameters: Ae and Fe% will be summarized and listed for urine faeces and total (Urine + Faeces)

Table 6 Statistical methodology specification

The following pharmacokinetic statistical analyses will only be performed if sufficient data is available (i.e. if participants have well defined plasma profiles).

Pharmacokinetic Statistical Analyses (Absolute Bioavailability assessment in Treatment Period 1)
Primary Endpoint / Variables

 AUC(0-t), AUC (0-∞) PK parameters of Plasma GSK3640254 (radiolabeled/non-radiolabeled) from IV and oral dose in Period 1 will be analyzed after log_e transformation (PK parameters should be divided by corresponding dose)
Model Specification

 Will be statistically analyzed using a mixed model (MM) for Period1. Terms fitted in the mixed effect ANOVA model will include: 
 Fixed effect : Treatment (IV dose/Oral dose in Period1) Random Effect : Subject The Kenward and Roger method for approximating the denominator degrees of freedom and correcting for bias in the estimated variance-covariance of the fixed effects will be used. Point estimates for the adjusted means on the loge scale, the mean difference between treatments and associated 90% confidence interval for the contrast (test-reference) will be constructed using the residual variance.

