Model Checking & Diagnostics

 Dose normalized PK parameters should be used for the analysis. For the Mixed Model analysis, Model assumptions will be applied, but appropriate adjustments maybe made based on the data. Distributional assumptions underlying the model used for analysis will be examined by obtaining a normal probability plot of the residuals and a plot of the residuals versus the fitted values (i.e. checking the normality assumption and constant variance assumption of the model respectively) to gain confidence that the model assumptions are reasonable. If there are any departures from the distributional assumptions, alternative transformations, such as data squared, or square root of data, will be explored.
Model Results Presentation

 The point estimate and confidence interval obtained from MM analysis will be exponentially back transformed to obtain Adjusted (least square) geometric means for each treatment. Point estimates (Absolute Bioavailability of GSK3640254) and associated 90% confidence interval for the ratio IV dose/Oral dose along with within-subject variability (%CVw) will be reported. Plots showing the adjusted geometric mean ratio(F) of IV dose to Oral dose in Period1 for AUC (0-∞) and AUC(0-t) together with 90% confidence intervals will be provided.

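### SAP Table 7 omits dose normalisation, so its 85 mg suspension to 200 mg tablet ratio is not relative bioavailability and the 0.80–1.25 rule is applied to the wrong quantity

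*SAP*

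**What the plan says.** Table 7 in SAP 5.4.2 sets out to estimate the relative bioavailability of the suspension: "compared to the 200 mg tablet, the PK parameters will be analysed using a mixed effect model as described below". The model for log AUC(0-inf), log AUC(0-t) and log Cmax has an intercept, a random participant effect, a treatment effect and residual error. The back-transformed results are geometric means of the parameters themselves, with their ratio and 90% CI.

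If the model does not converge, the fallback gives "paired-t test based 90% CIs for treatment difference in" the log scale, again from unadjusted values.

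The decision rule begins "The bioequivalence is established when the 90% CI of the ratio for" the AUCs and Cmax, and requires those intervals to lie within 0.80 to 1.25.

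The other bioavailability comparison in the SAP (5.2.2, Table 6) does ask for normalisation, twice: "PK parameters should be divided by corresponding dose" and "Dose normalized PK parameters should be used for the analysis". Table 6 covers only the Period 1 comparison of IV with oral dosing. SAP 5.4.1.2 refers back to Section 5.2 for how the parameters are reported, not for the Table 6 instruction, and the AUC and Cmax definitions in Table 4 are not dose-normalised.

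**The concern.** Relative bioavailability compares exposure per unit of dose. The two oral doses here are 85 mg and 200 mg, so a ratio of unadjusted exposures mixes the formulation effect with the dose difference. Limits of 0.80 to 1.25 on that ratio ask whether 85 mg gives the same total exposure as 200 mg, which is not the stated objective.

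Followed as written, the plan would put a ratio labelled as relative bioavailability, and a bioequivalence verdict, into the report. Neither would answer the formulation question. The rule would reject equally bioavailable formulations and could accept a suspension roughly twice as bioavailable as the tablet.

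**Working it through.** The documents give no expected ratio, power or sample-size figure for this comparison, so there is no stated number to reproduce.

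**Inputs**
- Doses: tablet 200 mg in Period 1, suspension approximately 85 mg in Period 2 (SAP 1.3; Protocol 4.1.1 and 4.1.2).
- Model, 90% CI and limits 0.80–1.25: SAP Table 7.
- Participants: about 6 enrolled, at least 4 completing both periods (SAP 1.3).
- Within-subject CV (CVw): not given; 10–40% assumed.
- Dose proportionality between 85 and 200 mg: not stated; assumed, then relaxed.

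**Expected ratio.** Let Frel be the true per-mg ratio, suspension to tablet. Under proportionality the raw ratio is Frel × 85/200 = Frel × 0.425. With Frel = 1 it is 0.425; inverted, it is 200/85 = 2.353. Both lie outside the limits.

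**Without exact proportionality.** If exposure scales as dose^b and the formulations are equally bioavailable, the raw ratio is 0.425^b: 0.504 at b = 0.8 and 0.358 at b = 1.2. It reaches 0.80 only at b = ln 0.80 / ln 0.425 = 0.26 or lower.

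**What the limits mean per mg.** 0.80/0.425 = 1.88 and 1.25/0.425 = 2.94. The raw rule can be met only around a per-mg ratio of 1.88 to 2.94.

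**Confidence intervals.** With complete data the two-treatment mixed model gives log(ratio) ± t(0.95, n−1) × σw × √(2/n), where σw = √ln(1 + CVw²). The table centres the intervals on 0.425 (raw) and 1.00 (normalised). The last column is the simulated probability (200,000 replicates) that the normalised CI falls within 0.80–1.25 when Frel = 1.

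| n | CVw | Raw 90% CI | Normalised 90% CI | P(rule met), normalised |
|---|---|---|---|---|
| 6 | 10% | 0.378–0.477 | 0.890–1.123 | 0.90 |
| 6 | 15% | 0.357–0.506 | 0.841–1.190 | 0.48 |
| 6 | 20% | 0.338–0.535 | 0.794–1.259 | 0.19 |
| 6 | 30% | 0.302–0.598 | 0.711–1.407 | 0.035 |
| 4 | 10% | 0.360–0.502 | 0.847–1.181 | 0.60 |
| 4 | 15% | 0.332–0.545 | 0.780–1.282 | 0.23 |
| 4 | 20% | 0.306–0.591 | 0.719–1.390 | 0.10 |
| 4 | 30% | 0.261–0.693 | 0.614–1.630 | 0.025 |

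On the raw scale with Frel = 1, the probability of meeting the rule is at most 0.0001 in every case, including CVw 40%. With Frel = 2.353 the raw rule is met with probability 0.90 (n = 6, CVw 10%).

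**Limit on what normalisation can achieve.** With a normalised point estimate of exactly 1, setting the half-width to ln 1.25 gives a maximum observed CVw of 19.4% for n = 6 and 13.5% for n = 4. If exposure is not proportional, equally bioavailable formulations give a normalised ratio of 0.425^(b−1): 1.19 at b = 0.8 and 0.84 at b = 1.2.

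**Rescaling check.** In one simulated set of six participants the raw ratio was 0.4346 and the normalised ratio 1.0225; 0.4346 × 200/85 = 1.0226, equal to rounding.

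**The case against.** The best defence is that the result would be literally true and easy to repair. Both doses appear in the arm labels, so an informed reader would not take 0.425 for a loss of bioavailability. With nominal doses the ratio and CI convert exactly on multiplying by 2.353. CL/F ("Apparent oral clearance, calculated as" dose over AUC(0-inf)) already carries the dose. The endpoint is exploratory, and SAP Section 2 states that there is no formal hypothesis. At CVw of 15% or more, four to six participants would more often than not miss 0.80–1.25 even after normalisation, so the verdict might not change. Finally, the SAP leaves data-handling detail to an Output and Programming Specification, which was not available and might contain the normalisation.

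Much of this stands, and it limits the importance of the point. It does not remove it. The SAP applies its rule to the unscaled interval. CL/F helps only for AUC(0-inf), and no planned parameter carries the dose for Cmax. Low power to meet the limits is a reason to report an estimate; it does not make the raw ratio a measure of relative bioavailability. A programming document cannot be relied on to correct a model and decision rule that the SAP itself sets out.

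**Conclusion.** The concern holds. Table 7 and its fallback leave out the dose normalisation that Table 6 requires, so the planned ratio does not measure the stated objective. Under dose proportionality it is too low by a factor of 0.425, and the bioequivalence rule is uninformative about formulation. The conclusion survives moderate departures from proportionality (0.50 to 0.36 for exponents 0.8 to 1.2).

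Whether the reported verdict would change depends on CVw, which the documents do not give; the ratio's value and meaning change at any CVw. This should be fixed before analysis, but it affects one exploratory comparison and no primary result.

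**What to change.** In Table 7 and in the paired-t fallback, divide each analysed AUC and Cmax by the dose given before the log transformation. Use the measured dose for the suspension and 200 mg for the tablet. Table 4's oral dose entry ("Radiometric oral dose calculated by" the analytical laboratory) is a radioactivity measurement and cannot apply to the unlabelled tablet, so the SAP should name the dose source for each arm.

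Report the suspension/tablet geometric mean ratio with its 90% CI. State that it assumes dose proportionality between 85 and 200 mg, and that formulation, dose and period cannot be separated in a "2-period, single-sequence" design. In line with SAP Section 2, present the result as estimation: either remove the claim that bioequivalence is established, or keep 0.80–1.25 only as a descriptive benchmark on the normalised values.

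The cost is one derived variable and a few lines of SAP wording, with no new data. The report gives up or softens a bioequivalence label.

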
 To generate samples that will be used to characterize the metabolite profile of GSK3640254 following a single IV microtracer dose of [¹⁴C]-GSK3640254 with an oral dose of non-radiolabelled GSK3640254 (plasma, urine, feces, duodenal bile) and a single, oral dose of [¹⁴C]-GSK3640254 (plasma, urine and feces, duodenal bile). 	
 Characterization and quantification of metabolites in plasma, urine, feces, and duodenal bile (qualitative identification in bile). These analytical investigations will be conducted, and the results reported under a separate GSK nonclinical protocol.

 To evaluate the PK and relative bioavailability of GSK3640254 following administration of the 85 mg suspension compared to the 200 mg tablet 	
 AUC(0-inf), AUC(0-t) and C_{max}

AUC(0–inf): Area under the plasma concentration-time curve from time zero (pre-dose) extrapolated to infinite time, AUC(0–t): Area under the plasma concentration-time curve from time zero (pre-dose) to last time of quantifiable concentration within a participant across all treatments, C_{max}: Maximum observed plasma concentration, t_{max}: time of occurrence of C_{max}, t_{1/2}: terminal phase half-life.

¹ For measured concentrations of GSK3640254 in plasma, the nomenclature [¹⁴C]-GSK3640254 describes the parent GSK3640254 concentration derived via analysis by liquid chromatography (LC) + AMS, whereas GSK3640254 describes the parent GSK3640254 concentration derived via liquid chromatography-tandem mass spectrometry (LC-MS/MS).

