4. STUDY DESIGN

4.1. Overall Design

This is a single group, single center, [¹⁴C]-GSK3640254 mass balance study with a two-period, single sequence, and no masking.

This open-label, single-center, non-randomised, 2-period, single-sequence, mass balance study will enroll a cohort of 6 healthy male participants. The aim of the study is to assess the pharmacokinetics, balance/excretion, and metabolism of GSK3640254 using [¹⁴C]-radiolabelled drug substance administered as an IV infusion of a microtracer dose with an oral tablet, non-radiolabelled dose (Treatment period 1) and a [¹⁴C]-radiolabelled drug substance administered orally (Treatment Period 2).

Four to six healthy participants are deemed sufficient. To minimise the number of exposed to radiation, participants who discontinue early will not be replaced unless the total number of participants who complete dosing and all critical assessments drops below 4.

Each participant will be involved in the study for up to 10 weeks. He will have a screening visit, two treatment periods (Treatment Periods 1 and 2), separated by a washout period of at least 13 days between oral doses, and a follow-up visit 7 – 14 days after the last assessment in Treatment Period 2. During both treatment periods, participants will reside in the unit from the morning of Day -1 until all procedures are completed at 168 h post-dose (on Day 8). Participants may be asked to stay for up to 1 week longer in Treatment Period 2, if excretion of drug-related material takes longer than anticipated (see [Figure 1](#)).

Safety data will include AE reporting, 12-lead ECG, vital signs, and laboratory safety tests. Blood will be sampled extensively on the day of dosing and daily until Day 8, for assessing the PK of GSK3640254 and metabolites.

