6.3. Measures to Minimize Bias: Randomization and Blinding

- This is an open-label study with no randomization and no blinding of participants, site personnel, or sponsor personnel.
- Eligibility will be established during the Screening Period. A cohort of six participants will be admitted to the clinical research unit on the same day and will complete Period 1 and Period 2 on the same schedule with the same study interventions. This approach minimizes potential bias associated with temporal effects.

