2. STATISTICAL HYPOTHESES / SUCCESS CRITERIA

This study is not designed for statistical testing and therefore has no formal statistical hypothesis.

Study objective will be evaluated descriptively and through estimation.

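### SAP Table 7 sets a bioequivalence rule for suspension versus tablet that a single-sequence study at two dose levels cannot support

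*SAP*

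**What the plan says.** Protocol section 3 lists an exploratory objective: "To evaluate the PK and relative bioavailability of GSK3640254 following administration of the 85 mg suspension compared to the 200 mg tablet". Its endpoints are AUC(0-inf), AUC(0-t) and Cmax. Bioequivalence does not appear in the objectives of either document.

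SAP section 2 states: "This study is not designed for statistical testing and therefore has no formal statistical hypothesis". It adds that objectives will be evaluated by description and estimation.

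For the suspension-tablet comparison, SAP section 5.4.2 says "the PK parameters will be analysed using a mixed effect model as described below". The model has an intercept, a random participant effect, a two-level treatment effect and residual error, fitted to the log of the PK parameter. There is no period or dose term and no division by dose. For the treatment difference, "its 90% CIs will be also estimated using the within-subject variance". Table 7 then gives a decision rule: "The bioequivalence is established when the 90% CI of the ratio for" the three parameters "are within the range of 0.80 to 1.25".

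On design, Protocol section 4.1 says: "This open-label, single-center, non-randomised, 2-period, single-sequence, mass balance study will enroll a cohort of 6 healthy male participants". The 200 mg tablet dose is given in Period 1 and the 85 mg suspension in Period 2, to everyone.

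Table 6 of the SAP, for absolute bioavailability within Period 1, does require dose-normalised parameters.

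**The concern.** A bioequivalence statement attributes a ratio to formulation. Here the two formulations differ, for every participant and in the same direction, in period and in dose level as well. The single treatment coefficient in Table 7 estimates the sum of these effects, yet the rule reads it as formulation alone.

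The rule also goes beyond what the study set out to do. An exploratory estimate of relative bioavailability needs a ratio and an interval. A pass/fail criterion is a test in substance, which SAP section 2 says the study was not designed for. The SAP's table of changes to the protocol-defined analysis (section 1.1) lists only the added Enrolled population.

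At stake is a sentence in the study report saying that bioequivalence was, or was not, established. Neither sentence would be supported by the data.

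**Working it through.** The documents give no power, within-subject CV, period effect or dose exponent, so there is no stated figure to reproduce. The check covers identifiability first, then size.

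**Inputs from the documents.** Doses 85 mg and 200 mg; one sequence; six participants enrolled with at least four completers; 90% CI; limits 0.80 and 1.25. **Assumed:** within-subject CV of 10% to 40%, exponent b, and period effect k.

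**1. Identifiability.** For participant i, the log difference (suspension minus tablet) is

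d_i = formulation + period + dose effect + error.

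Only the sum of the first three is estimable. In matrix form, six participant columns plus one period and one formulation column make 8 columns with rank 7, and period and formulation correlate at 1.0. A two-sequence crossover would give rank 8 and correlation 0. Dose level repeats the same column. Adding a period or dose term to Table 7 therefore cannot help.

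**2. As written, with no dose divisor.** With equal formulations, proportional PK and no period effect:

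- Expected ratio = 85/200 = 0.425.
- For the expected ratio to fall inside the limits, the suspension would have to be between 0.80/0.425 = 1.88 and 1.25/0.425 = 2.94 times as bioavailable as the tablet.
- The probability that one parameter meets the rule, using a paired 90% CI with n - 1 degrees of freedom and standard error s_w × sqrt(2/n), is 0.0001 or less for n = 4 or 6 and CV 10% to 40%.

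**3. With dose normalisation added.** If exposure varies as dose^b and the formulations are identical, the ratio is 0.425^(b-1):

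| b (assumed) | ratio |
|---|---|
| 0.8 | 1.19 |
| 0.9 | 1.09 |
| 1.0 | 1.00 |
| 1.1 | 0.92 |
| 1.2 | 0.84 |

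The ratio itself leaves the limits when b < 1 + ln(1.25)/ln(0.425) = 0.74 or b > 1 + ln(0.80)/ln(0.425) = 1.26.

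**4. Period effect after normalisation.** A multiplicative period effect k passes one-for-one into the ratio. With n = 6, CV 10%, proportional PK and a true formulation ratio of 0.80 (on the boundary, so not equivalent), the probability that one parameter is declared equivalent is:

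| k (assumed) | expected ratio | probability of passing |
|---|---|---|
| 1.00 | 0.80 | 5% |
| 1.10 | 0.88 | 41.5% |
| 1.15 | 0.92 | 67% |
| 1.25 | 1.00 | 90% |

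These probabilities fall as CV rises, because the interval becomes too wide to fit. At CV 30% the last row is 3.5%.

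**The case against.** The strongest reply is that the analysis is exploratory, the single sequence and the doses are openly stated, and Table 7 labels each arm with its dose. The rule is also conditional, and the analysis runs only if the data suffice. All of this is true, and it limits the importance of the point. It does not rescue the rule, because disclosing the design does not make the formulation effect estimable.

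A second reply is that ratios of 0.84 and 1.19 lie inside 0.80 to 1.25, and that the exponents are hypothetical. The exponents are indeed assumed, and the earlier ascending-dose study may hold evidence on proportionality that is not shown here. But the rule applies to the interval. At n = 6 with an estimated CV of 10%, the half-width on the log scale is 2.015 × 0.0998 × sqrt(2/6) = 0.116, a factor of 1.123. Then 0.843/1.123 = 0.75 and 1.187 × 1.123 = 1.33, so both cases fail with no formulation difference.

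A reader might infer more than the documents support:

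- **That the SAP as written risks a false claim of bioequivalence.** Without a dose divisor, passing is almost impossible under proportionality and equal formulations. That risk arises only once normalisation is added.
- **That the Period 1 infusion matters too.** It is 100 µg beside 200 mg, or 0.05% by mass. At the 15% bioavailability assumed in Protocol section 4.3 it is 0.1/(0.15 × 200) = 0.33% of systemic drug. The half-hour difference in the food cue has no documented PK effect.
- **That assay batches coincide with periods.** Neither document says so.
- **That Protocol section 6.3 is wrong in saying** "This approach minimizes potential bias associated with temporal effects". It describes keeping participants on one schedule and makes no claim about the formulation contrast. The alias comes from the single sequence and would remain if entry were staggered.

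**Conclusion.** The point holds. The Table 7 rule asks for a conclusion about formulation from a contrast in which formulation, period and dose level are one and the same column. This follows from the design alone and rests on no assumed value.

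The size depends on whether dose normalisation is added. As written, the likely result is a failure driven by the 85 versus 200 mg difference (expected ratio 0.425 under proportionality, equal formulations and no period effect), which says nothing about formulation. With normalisation, both a pass and a failure become possible for reasons unrelated to formulation. The figures illustrating this use assumed exponents, period effects and CVs, and show what could happen rather than what is expected.

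The consequence is confined to an exploratory objective. Absolute bioavailability is compared within Period 1, and that analysis, the mass balance and the other primary objectives are not affected.

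**What to change.** In SAP section 5.4.2:

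1. Delete the bioequivalence criterion from Table 7.
2. Divide each parameter by its dose before taking logs, as Table 6 does, and do the same in the paired fallback analysis.
3. Report the geometric mean ratio and 90% CI as a descriptive estimate, labelled as 85 mg suspension in Period 2 versus 200 mg tablet in Period 1.
4. State in the table footnote and the study report that formulation, dose level and period cannot be separated and that no equivalence conclusion is drawn.

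The cost is a change to SAP text and one table footnote. The protocol, including section 6.3, needs no change, and no data or samples are affected. What is lost is an equivalence statement that no objective asks for.
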